**Ecological Momentary Assessment (EMA)**

Participants provided daily ecological momentary assessment data (meaning data that has been collected “in the moment”) for 4 weeks total during the study. Participants were sent a text message that contained a link to an online survey that they could complete on their mobile smartphone. For most of the EMA portion of the study, participants were sent 3 assessments per day (morning, midday, and evening). Daytime EMA assessments were brief (<5 min) to include the brief WSWS2-B (and exploratory items: anhedonia, pain) and additional items focused on understanding the motivationally relevant affective/cognitive subjective states associated with withdrawal and craving (e.g., wanting to reduce stress, to feel a high or buzz), smoking (# cigarettes), and smoking triggers since the last EMA survey. The evening assessment included a larger battery of questionnaires to include the WSWS2-B and additional targeted assessments regarding smoking, person-related, and contextual factors in the last 24 hours. These evening assessments (1x/day) included smoking (# cigarettes), e-cigarette use (yes/no), alcohol use (yes/no, quantity), cannabis use (yes/no, mode of use, tobacco co-administration), pain (worst), cessation confidence and self-efficacy, smoking triggers (e.g., stressful events, cigarette access, others smoking) and coping strategies, future smoking likelihood/prediction, and NRT medication use (e.g., yes/no, mini lozenge quantity, subjective effects). The frequency of EMA increased to 6 reports/day for 5 days from 1-day pre-TQD to 3-days post-TQD in order to provide intensive monitoring of withdrawal symptoms on a more fine-grained time course during the early period of abstinence. Participants completed the full WSWS2-L (rather than the WSWS2-B) during the evening EMA during these 5 days (1x/day). Participants were compensated \$100 for completing >80% of the EMA assessments. Payments were linked to assessment completion, but not to smoking status so as not to induce participants to incorrectly report their smoking status.

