**Table 3. Ecological Momentary Assessment (EMA) & Combination Nicotine Replacement Therapy (C-NRT) Schedule**

	Pre-cessation	TQD	Cessation	
EMA Assessments (29 days)	3/d (13 days) TQD -14 to -2	6/d (5 days) TQD -1 to +3	3/d (11 days) TQD +4 to +14	No EMA TQD $\geq$ 15
Medication Status	No Medication		C-NRT TQD $\sim$ +8 to 63 (Start Day After Visit 2)	

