## Data Analysis Plan

### WSWS2 & MTWS-R Scoring:

The WSWS2-L (Smith et al., 2021) is a 19-item scale scored via one total score (mean) and 6 subscale scores (means). The WSWS2-B is a 6-item scale scored as one total score (mean). The WSWS2-L was assessed at all study phone calls and in-person visits (see Table 1-2 for assessment timeline). The brief version (WSWS2-B) was assessed at all EMA reports (3-6x/day), with the exception of TQD -1d through TQD +3d, while the long version (WSWS2-L) was assessed at the evening report (the WSWS2-L comprises the WSWS2-B items). Also see *Exploratory Withdrawal Symptoms* section below.

The MTWS-R is a 17-item scale with one item per symptom domain and no subscales. We will score one total score (mean) of the first 8-items that are DSM-5 symptoms as our primary MTWS-R score. We will score an exploratory MTWS-R including all 17-items (mean) that includes 'other possible symptoms' of smoking withdrawal. The MTWS-R and related information was derived from John Hughes UVM website describing the scale:

<http://www.med.uvm.edu/behaviorandhealth/research/minnesota-tobacco-withdrawal-scale>

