In order to understand how short periods of abstinence might affect baseline (pre-cessation) scores and the pre-to-post jump in withdrawal, additional analyses will be undertaken to select pre-withdrawal scores that have occurred within 15 or within 30 minutes of smoking a cigarette during the baseline period. These will be used to generate pre-withdrawal or baseline estimates and then used in piecewise models to determine the pre-to-post cessation changes in withdrawal scale and subscale scores. This may constitute a more sensitive test of abstinence related withdrawal than will use of unselected baseline scores (e.g., all evening reports). Also, the relations of time-since-smoking data collected in the baseline period will be used as time varying covariates to study the relations of this with withdrawal severity in the same baseline reporting episode.

*Internal Consistency, Temporal Stability, Item Analysis, & Factor Structure:*

WSWS2-L total scale and subscale internal consistency will be assessed with Omega (McDonald, 1999) with bootstrap-corrected 95% confidence intervals (CIs). For comparison, we will also compute Cronbach's alpha coefficient (Cronbach, 1951). Ideally, both omega and alpha will be  $> 0.7$  for total scale and subscale at all timepoints. Further, we will examine response distributions and item-to-total correlations and subscale to total correlations. We will conduct parallel analyses for the WSWS2-B total scale (but with no subscale analyses).

We will examine internal consistency pre-TQD and at multiple timepoints post-TQD. We will examine internal consistency at Visit 1, which provides the largest sample size of participants pre-quit. We will examine internal consistency on the TQD (i.e., EMA evening report), TQD +1 to 2d (i.e., Call 4), and TQD +1w (i.e., Visit 2). This will provide estimates and comparison of the internal consistency at critical time points and assessment modalities (e.g., EMA mobile phone self-report, phone call with study staff, in-person tablet self-report) within the first week of the quit attempt.

We will examine the idiographic variability or lability of scales and subscales across the pre-TQD period. This will be compared with such variability in the post-quit period. Regression analyses will also be used to determine associations and shared variance during the pre-cessation period between Visit 1 (TQD  $>-2w$ ) and Call 1 (TQD -12d) and between Call 1 to Call 2 (TQD -7d).

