We will conduct Confirmatory Factor Analyses (CFA) following the approach we took during the initial development and validation of the WSWS2 (Smith et al., 2021). We will conduct CFAs with a maximum likelihood (ML) estimator and allow factors to correlate. We will use the following model goodness of fit statistics to evaluate CFA models (Hu & Bentler, 1999): a) root mean square error of approximation (RMSEA) with values  $<.06$  indicative of good fit, b) comparative fit index (CFI) with values  $>.95$  indicative of good fit, c) Tucker-Lewis index (TLI) with values  $>.95$  indicative of good fit, and d) standardized root mean residual (SRMR) with values  $<.08$  indicative of good fit. Ideally the WSWS2-L will display a simple structure (e.g., relatively low cross-loading of items on subscales). We will examine a 6-factor model and a single higher-order factor model for the WSWS2-L and a 1-factor model for the WSWS2-B. We will examine factor structure both on the TQD (via EMA evening report) and 1-week post-TQD in-person assessment (Visit 2).

We will conduct similar internal consistency and item analyses on the MTWS scales excepting the subscale analyses.

*Network Analysis (Exploratory):*

As a complementary perspective on measurement, we will apply Gaussian graphical network models to examine possible interactions between individual symptoms of withdrawal, both for the WSWS2-B, WSWS2-L, and MTWS-R. We will approach such analyses with the intent of evaluating (1) similarities of network structure among WSWS2-B, WSWS2-L, and MTWS-R and (2) evaluating possible change in network structure and/or the relations between individual symptom pairs (edges) in the presence of abstinence. These analyses will be based on the estimated inter-item polychoric correlation matrices of the respective scales and apply LASSO regularization in the evaluation of edge weights within the networks.

*Convergent and Concurrent Validity:*

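### No omega, alpha, item-total analysis or CFA of the WSWS2-B is specified on a brief-form administration, and its evening quit-day jump is largely confounded with a change of form

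*SAP*

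**What the plan says.** The SAP section on internal consistency and factor structure names Visit 1 as the pre-quit occasion for reliability and adds "internal consistency on the TQD (i.e., EMA evening report), TQD +1 to 2d (i.e., Call 4), and TQD +1w (i.e., Visit 2". For the brief form it says only "We will conduct parallel analyses for the WSWS2-B total scale (but with no subscale analyses", without giving occasions of its own. The same section plans "a 1-factor model for the WSWS2-B", with factor structure examined at the TQD evening report and at Visit 2.

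Two other SAP sections fix which form was answered on those occasions:

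- WSWS2 & MTWS-R Scoring: "The WSWS2-L was assessed at all study phone calls and in-person visits". The brief form was used in EMA "with the exception of TQD -1d through TQD +3d, while the long version (WSWS2-L) was assessed at the evening report". The section adds that "the WSWS2-L comprises the WSWS2-B items", so a brief score can be computed from any long-form record.
- Ecological Momentary Assessment, on TQD-1 to TQD+3: "Participants completed the full WSWS2-L (rather than the WSWS2-B) during the evening EMA during these 5 days (1x/day".

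Under Sensitivity to Abstinence, evening EMA reports feed piecewise models of the TQD jump, for which the one-week pre-quit mean is the example reference. The section also plans a comparison of the weeks before and after quitting, and post-quit trajectories over three days and one week. It allows the last 1-3 pre-quit days to be left out of the baseline if scores rise in anticipation. No adjustment for the change of evening form is stated.

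**The concern.** The SAP's Significance section justifies the short form by settings in which the long form is not practical. In such settings respondents see the brief form only. Coefficients computed on six items extracted from a 19-item administration do not directly establish reliability or one-factor structure for that use. The right data exist but no reliability or CFA occasion points to them.

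The second issue concerns Aim 1, sensitivity to abstinence. The SAP hypothesizes that the WSWS2-B rises over the first three days and the first week. In the evening series the form changes one day before the quit day. If answering the items within the long form shifts their mean, part of the estimated jump is a form effect. A shift starting at TQD-1 could also look like anticipatory withdrawal and so influence whether those days stay in the baseline.

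**Working it through.** **1. The schedule.** SAP Table 3 gives "EMA Assessments (29 days" in three blocks: 13 (TQD-14 to -2) + 5 (TQD-1 to +3) + 11 (TQD+4 to +14) = 29, as stated. The middle block is long form in the evening, the outer two brief. Brief-form evenings: 13 + 11 = 24 of 29.

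**2. Form at each named occasion.**

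| Analysis | Named occasions | Form answered | Brief-form occasions |
|---|---|---|---|
| Omega, alpha | Visit 1, TQD evening, Call 4, Visit 2 | Long at all | 0 of 4 |
| CFA | TQD evening, Visit 2 | Long at both | 0 of 2 |
| Stability regressions | Visit 1, Call 1, Call 2 | Long at all | 0 of 3 |

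The item-total analysis names no occasions of its own.

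**3. Form effect in the evening contrasts.** Let c be the shift in the six-item mean from answering within the long form. It is an assumption: the documents give neither size nor sign. The contribution to a contrast of means is c × (long-form share after − long-form share before).

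- Baseline week TQD-7 to TQD-1: 1 of 7 evenings is long form, a share of 1/7.
- TQD evening: share 1. Jump: c(1 − 1/7) = 6c/7 ≈ 0.86c.
- Last 1, 2 or 3 pre-quit days dropped: baseline share 0. Jump: c(1 − 0) = c.
- Week means, post-quit week TQD to TQD+6: c(4/7 − 1/7) = 3c/7 ≈ 0.43c.
- Week means, post-quit week TQD+1 to TQD+7: c(3/7 − 1/7) = 2c/7 ≈ 0.29c.
- Week means with TQD-1 dropped: 3c/7 to 4c/7, that is 0.43c to 0.57c.
- Trajectory TQD to TQD+3: all four evenings are long form, so nothing is added.
- First-week linear slope: regressing the long-form indicator on day gives −6/28 = −0.21c per day over TQD to TQD+6, and −8/42 = −0.19c per day over TQD to TQD+7.

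**4. A form-matched alternative.** Evenings TQD-7 to TQD-2 (six) and TQD+4 to TQD+7 (four) are all brief form: c(0 − 0) = 0. On the planned schedule all ten precede C-NRT, which starts the day after Visit 2.

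**The case against.** A reader might infer that the brief form is never tested for reliability or structure. The documents do not support that. The convergent-validity section correlates long-form call and visit scores with brief-form EMA scores on the days of Call 1, Call 2, Call 4 and Visit 2; on three of those days (TQD-12, -7, +7) the evening report was brief form. The lability and exploratory network analyses name no administration and could use brief-form evenings. These analyses do not replace the missing tests: a Pearson correlation is blind to a constant mean shift and yields no omega or factor fit, lability is not internal consistency, and the network work is exploratory.

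A reader might also infer that the form switches on the quit day itself. It switches at TQD-1, so the step from TQD-1 to TQD is form-matched, though with a single long-form pre-quit evening. The call and visit comparison of pre- and post-quit scores is long form throughout. It is planned for the WSWS2-L and shows whether a rise appears with form held constant, but it does not test the brief form.

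Four further points stand:

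- Nothing shows that c differs from zero, and item order is not documented, so no claim about neighbouring items can be made.
- Brief-form reports also carried two anhedonia items and one pain item, and the evening report had a larger battery. The added analyses would therefore test the brief form without the long form, not six items in isolation.
- The SAP gives reasons for its occasions (largest pre-quit sample, critical times, different modalities). Ranking brief-form evenings above them would be a preference.
- The MTWS-R is scheduled at calls and visits and is not listed in EMA, so a same-occasion comparison with the brief form was not available.

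**Conclusion.** The point holds in two parts. First, every omega, alpha and CFA occasion named for the WSWS2-B (four and two respectively) is a long-form administration, and no item-total analysis is placed on a brief-form one, despite 24 scheduled brief-form evenings. This follows directly from the SAP and needs no assumption. Second, the WSWS2-B evening jump is largely confounded with form: 6c/7 with the full baseline week, c after trimming. The week-mean comparison carries about a third to under a half of c with the full baseline week, and the three-day trajectory none. This part is conditional on c, which may be zero; it identifies a bias that the plan cannot rule out, not one shown to exist. The matter is a worthwhile, cheap improvement that affects what can be concluded about the brief form. It does not invalidate the planned analyses.

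**What to change.** 1. Keep the planned occasions, but label their WSWS2-B results as items taken from the long form.
2. Add WSWS2-B omega, alpha, item-total analysis and the one-factor CFA on at least one pre-quit brief-form evening (for example TQD-7) and one unmedicated post-quit brief-form evening. TQD+7 is a good choice because it is the Visit 2 day and allows a direct comparison with the extracted items. Use evening reports: the protocol's EMA section omits sleep from daytime prompts, so only the evening carries all six items.
3. Beside the planned TQD jump, report the form-matched WSWS2-B contrast of evenings TQD-7 to TQD-2 against TQD+4 to TQD+7.
4. State the form change at TQD-1 as a caveat when judging anticipatory rise and deciding which pre-quit days to exclude.

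The cost is some SAP wording and a few extra model runs, with no new data. The form-matched contrast misses TQD to TQD+3 and may fall past the withdrawal peak, so it supplements the planned jump and does not replace it.

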### **Analytic Plan**

#### **Specific Aims: WSWS-2 and WSWS-2BR Validation**

Psychometric analyses of the 18 item pool will be conducted to validate a full and brief version (6 items) of the WSWS2 in this sample of medicated and unmedicated smokers. The aims include clarifying the dimensional structure and the best-performing items to construct the final scales. Subscales will be evaluated with respect to internal consistency (e.g., Cronbach's alpha  $\geq .8$ ), item-analysis (response distributions, item-to-total correlations, IRT analyses), and confirmatory factor analyses (CFA) and measurement invariance (e.g., across at least 2 post-TQD time points).

Concurrent, discriminant, and predictive validity will be considered in evaluating and constructing the final scale. The WSWS2-L should demonstrate meaningful relations with measures of tobacco dependence (WISDM-PDM, FTCD, time to first cigarette), other published withdrawal scales (Minnesota Withdrawal Scale), and prediction of cessation outcomes (e.g., time to lapse/relapse, survival analyses). In analyses predicting cessation outcomes both pre-post increase in withdrawal symptoms and post-TQD symptoms per se will be used in prediction models. In addition, such models will be tested with and without (primary) covariates (gender, and race). The WSWS2-L should demonstrate a characteristic time-course of a withdrawal syndrome including sensitivity to abstinence (rise over first 12-24 hours and 2-4 days) and decrease over time following a peak in post-TQD. The time course will be examined with growth curve models that evaluate different trajectory components (i.e., linear, quadratic) with time

varying covariates for smoking lapse occurrence, exposure to temptation events, dependence level. The WSWS2-L should also be sensitive to medication use (e.g., decrease with C-NRT). This will be tested by determining the effects of C-NRT during Cessation on WSWS2-L scores versus precessation and unmedicated cessation levels. The WSWS2-L will be correlated with variables that assess relevant person factors such as affective disorder, distress tolerance, and the various measures of tobacco dependence.

We will conduct parallel set of psychometric and validation analyses of the WSWS2-B as we do with the WSWS2-L, except when not possible due to constraints placed on single-item subscales (e.g., subscale internal consistency, CFA).

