### Sensitivity to Abstinence:

The WSWS2 (-L and -B) should demonstrate a sensitivity to abstinence from smoking. We will examine whether WSWS2 total and subscale scores display significant increases from pre-quit to post-quit using a series of linear models. First, using EMA data (evening report) we will use piecewise models that allow for discontinuity (pre- vs post-quit day) to examine within-person changes in WSWS2 (-L and/or -B) from pre- to post-quit. We will examine differences in mean withdrawal severity during the week before vs after the quit-day, modeling the TQD jump (e.g., from 1w pre-quit mean to TQD) and post-TQD trajectory (e.g., slope, quadratic) over the first 3 days (WSWS2-L and WSWS2-B) and first week (WSWS2-B). Using study call/visit data we will examine within-person changes in WSWS2-L from an averaged baseline (averaged across pre-TQD calls/visits) to TQD +1-2d (Call 4) and TQD +1w (Visit 2). For EMA and Call data, we will examine the stability of baseline scores with and without approximately 1-3 days pre-quit to determine if there are anticipatory increases in withdrawal shortly before the TQD (and therefore exclude that rise from mean baseline calculations). We will examine sensitivity of WSWS2 to detect effects of smoking abstinence on withdrawal severity among the entire study sample as well as only among participants who self-report smoking no more than 2 cigarettes in the past 24 hours during the post-TQD timepoints as these individuals should still be experiencing significant withdrawal. We will examine several cigarettes/day cutoffs in sensitivity analyses to determine the robustness of results as function of this exclusion criterion (see below for *Sensitivity Analyses*). We hypothesize that both the WSWS2-L and the WSWS2-B will increase

significantly during the first 3 days and first week post-quit relative to pre-quit baseline values. Further, we expect increases to vary across the WSWS2-L subscales; we expect to see especially large increases in WSWS2-L subscales assessing craving, hunger, and concentration difficulties.

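### The SAP reads pre- to post-quit rises in WSWS2 scores as sensitivity to abstinence but plans no test that the items work the same way before and after quitting; the exposure is mainly in the subscales.

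*SAP*

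**What the plan says.** The central validity test is in the SAP under Sensitivity to Abstinence: "We will examine whether WSWS2 total and subscale scores display significant increases from pre-quit to post-quit using a series of linear models". The same section predicts a pattern across subscales: "we expect to see especially large increases in WSWS2-L subscales assessing craving, hunger, and concentration difficulties". It describes two data sources. The first is the evening EMA report, analysed with piecewise models around the TQD. The second is the study contacts, where a baseline averaged over pre-TQD calls and visits is compared with Call 4 (TQD +1 to 2 days) and Visit 2 (TQD +1 week).

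The factor analyses come under Internal Consistency, Temporal Stability, Item Analysis, & Factor Structure. The models are these: "We will examine a 6-factor model and a single higher-order factor model for the WSWS2-L and a 1-factor model for the WSWS2-B". They are judged by RMSEA, CFI, TLI and SRMR. Two occasions are named: "We will examine factor structure both on the TQD (via EMA evening report) and 1-week post-TQD in-person assessment (Visit 2"). The SAP does not mention invariance. It refers the general approach to an earlier study: "We will conduct Confirmatory Factor Analyses (CFA) following the approach we took during the initial development and validation of the WSWS2".

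The protocol's Analytic Plan does list an invariance analysis: "confirmatory factor analyses (CFA) and measurement invariance (e.g., across at least 2 post-TQD time points").

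**The concern.** Comparing observed means before and after quitting assumes that an item has the same loading and intercept on both occasions. If an item is answered differently after the quit day, or in a different mode, at the same level of withdrawal, the subscale mean moves although the construct has not. The trial has one group, so no control arm would show such a shift.

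What is at stake is the reading of the subscale results, and above all the predicted ordering of craving, hunger and concentration. With few items per subscale, one item can carry much of a difference. The planned CFAs cannot show this. Neither is pre-quit, neither constrains parameters across time, and they differ in mode as well as in time (EMA against an in-person visit), so comparing them informally would not separate the two.

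**Working it through.** **1. Where the documents leave the gap**

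| Check in the plan | Pre-quit? | Tests equal intercepts? |
|---|---|---|
| CFA, TQD evening EMA | No | No |
| CFA, Visit 2 | No | No |
| Omega and alpha at Visit 1, TQD, Call 4, Visit 2 | Yes | No (reliability) |
| Item distributions, item-total correlations | Yes | No |
| Exploratory network models | Change under abstinence | No (correlation matrices only) |
| Protocol invariance analysis | Example is post-TQD only | Not specified |

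**2. Which pre/post analyses are exposed**

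- Evening EMA: one mode before and after the TQD, so mode mixing does not arise. The evening report carried the long form only from TQD -1 to TQD +3, so it gives one pre-quit evening of long-form subscale scores. The SAP may exclude about 1 to 3 pre-quit days from the baseline for anticipatory rise. Long-form subscale change therefore leans on the call/visit data.
- Calls and visits: the averaged baseline combines Visit 1 with the pre-TQD calls. The SAP itself distinguishes staff phone calls from in-person tablet reports. Under the protocol a missed Visit 2 may also be done by phone.

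**3. Size, for illustration**

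The plan gives no figure to reproduce. From the SAP: 19 items, 6 subscales (19/6 = 3.2, taken as 3) and N = 232 enrolled. Assumed: a shift of 0.25 or 0.5 points in one item, no true change in withdrawal, and an SD of change of 1 point, with 0.6 as an alternative.

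- Shift in the mean = item shift / number of items
- SE = SD / sqrt(N) = 1 / sqrt(232) = 0.066
- P(significant) = Phi(shift/SE - 1.96) + Phi(-shift/SE - 1.96)

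| Score | Item shift | Shift in mean | P, SD 1.0 | P, SD 0.6 |
|---|---|---|---|---|
| 3-item subscale | 0.25 | 0.083 | 25% | 56% |
| 3-item subscale | 0.5 | 0.167 | 72% | 99% |
| 6-item WSWS2-B | 0.25 | 0.042 | 10% | 19% |
| 6-item WSWS2-B | 0.5 | 0.083 | 25% | 56% |
| 19-item total | 0.5 | 0.026 | 7% | 10% |

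For the subscale at SD 1, the shifts are 0.083/0.066 = 1.3 SE and 0.167/0.066 = 2.5 SE. N = 232 is enrolment, not pre/post completers. At an assumed N = 150, SE = 0.082 and the ratios fall to 1.0 and 2.0 (P = 18% and 53%).

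**4. What model size the data can carry**

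Parameters in the configural model, with residuals of the same item correlated across occasions:

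- Three occasions, 19 items, 6 factors: 39 loadings + 171 factor variances and covariances + 57 residual variances + 57 residual covariances + 57 intercepts = 381, more than the 232 participants.
- Two occasions, 19 items: 38 + 66 + 38 + 19 + 38 = 199, or 232/199 = 1.2 participants per parameter.
- Two occasions, one 3-item subscale: 6 loadings + 1 factor correlation + 6 residual variances + 3 residual covariances + 6 intercepts = 22, or 10.5 per parameter. Moments: 21 + 6 = 27, so 5 df.
- Two occasions, one-factor WSWS2-B: 12 + 1 + 12 + 6 + 12 = 43, or 5.4 per parameter. Moments: 78 + 12 = 90, so 47 df.

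Testing by subscale is practical; a joint model is not.

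**The case against.** The strongest reply has four parts.

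- The first-listed analysis, evening EMA against evening EMA, is in one mode. This stands. A reader might infer that every pre/post comparison mixes modes; only the call/visit analysis does.
- A reader might also infer that the SAP withdrew a promised pre/post test. The documents do not support that. The protocol's wording, "measurement invariance (e.g., across at least 2 post-TQD time points"), gives a post-TQD example and names no pre/post test. The SAP calls its registration complementary and more detailed, and does not say that it replaces the protocol. The development study whose CFA approach it adopts may have included invariance, which cannot be checked from these documents. What can be said is that the SAP is silent and that neither document explicitly plans a pre/post test.
- The size rests on assumed shifts and SDs. This stands too. At SD 1 the smaller shift does not reach significance on its own, and the hypothesis stated first concerns the overall long and brief forms, where one item matters less.
- The plan has related safeguards: reliability before and after quitting, cross-modality correlations, baselines taken soon after smoking, and subsets restricted by smoking. They mean that the claim does not rest on one mean difference alone, but none of them tests intercepts.

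An intercept shift may also be a real, item-specific response to abstinence. It would therefore qualify the reading of a subscale rise, not refute it.

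**Conclusion.** The point holds in a limited form. Observed pre/post change is read as sensitivity to abstinence with no planned test that the measurement is comparable. The exposure lies mainly in the long-form subscales, where the predicted ordering sits, and in the call/visit analysis with its pooled visit and phone baseline.

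Under the assumptions shown, one item shifting by 0.5 points could make a three-item subscale rise look significant (about 2.5 SE). A 0.25-point shift would usually not do so at SD 1, and the 19-item total is barely affected. The documents give no evidence that such shifts occur. They do not support a conclusion that the expected rises would be artefacts or that the overall sensitivity claim fails. The observed-change analyses can stay. This is an inexpensive improvement bearing on the main validity claim, and it would also settle the status of an analysis that the protocol already lists.

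**What to change.** 1. State in the SAP whether the protocol's invariance analysis stands and on which occasions. Date the addition and say whether item-level data had been examined by then.
2. Add configural, equal-loading and equal-intercept tests, subscale by subscale for the WSWS2-L and for the one-factor WSWS2-B, with the decision rule fixed in advance.
3. Use same-mode pre/post pairs: Visit 1 against Visit 2 (setting aside or flagging any Visit 2 done by phone), a pre-quit call against Call 4, and pre- against post-quit evening EMA for the WSWS2-B.
4. Where intercepts differ, report the latent mean change under partial invariance beside the observed change, and qualify the sensitivity claim for that subscale.
5. Do not fit the three-occasion, 19-item model: about 381 parameters for 232 participants, and it would mix phone with tablet.

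The cost is modest analysis work on data already collected, and possibly a caveat on some subscales.
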